### **3.3.3 Instruments – Outcome measurement variables**

The outcome measurements chosen for this study assessed the patients' progress during their physical therapy episode of care on various levels. Patient reported outcomes assessed clinical pain and functional progress by utilizing the Oswestry Disability Index 2.0 (ODI), Numeric Pain Rating Scale (NPRS), and a Global Rate of Change Scale (GROC) as these have been shown to be more responsive than physical impairment measurements.

Oswestry Disability Index 2.0: Improvement in function is a key outcome measurement for clinical conditions and the ODI has shown to have some of the best responsiveness when it comes to patients with low back pain. The ODI has been an extensively used measurement tool to evaluate function and how back pain affects an individual's ability to do daily activities. The ODI assesses function in 10 categories (pain intensity, personal care, lifting, walking, sitting, standing, sleeping, sexual activity, social life, and traveling). Version 2.0^135 was utilized for the purposes of this study. Each of the 10 categories has six statements that are scored from 0 to 5, the statement with the least disability is scored a 0 and the greatest disability scored with a 5. If more than one statement is marked, then the highest score is recorded. The overall score (index) is calculated by taking the total points added up for items answered and dividing by the total possible score (number of categories answered x 5). This number is then multiplied by 100 and rounded to a whole number. Overall index scores can be interpreted for

the range of 0-20% for minimal disability, 21-40% for moderate disability, 41-60% for severe disability, 61-80% for crippled, and 81-100% for individuals bed bound or exaggerating their symptoms. (Appendix I)

Numeric Pain Rating Scale: The NPRS is a unidimensional measurement of pain intensity in adults. It consists of an 11-point ordinal scale measuring pain from “0” = no pain to “10” = worst pain imaginable. The respondents were asked to report on current, best and worst pain in the last 24 hours. All three scores (current, best, and worst) were recorded along calculation of the average of all three being reported. This scale has been used across various diagnoses and age ranges. (Appendix J)

Global Rate of Change scale: The GROC scale, as stated in its name, is global rating of improvement and satisfaction over the course of treatment. It does not measure a specific dimension such as pain or function, but allows the patient to decide what they consider important. The GROC is a commonly used outcome tool in clinical research, especially as it relates to musculoskeletal care. The most common formats of the GROC is typically a 7, 11, or 15 point scale on a number line with 0 in the middle and moving out one integer in the positive and negative numerical direction. The end anchors also contain the negative and positive words of “very much worse” and “very much improved” or “completely better” with “no change” being in the middle at the zero. Evidence shows that scales with 7 or 11 points offer the best mix of patient preference, appropriate discrimination ability, and test-retest reliability. For purposes of this study the recommended 11-point scale was used (-5 = very much worse, 0 = unchanged, 5 = completely recovered). (Appendix K)

### **3.3.4 Instruments – Demographic collection**

Demographic data was collected on both the patient along with the treating physical therapists involved in providing care. Each patient provided information regarding age, gender, race, and educational level. The patient's birth order was recorded, as first born or only child have been shown to accept treatment more readily and stayed in treatment longer. Questions related to whether the patient had been seen in physical therapy previously, at this specific site, or by this specific therapist was enquired upon during the initial demographics screening. Lastly, the choice of why the patient participant selected physical therapy, the specific clinic, and physical therapist was asked. (Appendix B) Each of the participating physical therapists also completed a demographics form providing their age, gender, race, level of physical therapy education, specialty certifications (if any), and years practicing as a physical therapist.

(Appendix L)

### **3.3.5 Procedural process**

Clinical sites across the US were recruited to be data collection sites. These sites were chosen based on interest in participating with research design and availability to be a data collection site. Physical therapists at each location were given the option to opt in or out as a participating physical therapist. If the physical therapist opted in, they signed an informed consent and completed a physical therapist participant demographic information form and were provided a coded ID#.

At each clinical site, front office staff that recognized potential patients for the study (patients being seen for initial evaluation of low back pain or equivalent diagnosis by a physical therapist that had consented to partake in the study) gave the patient a research study recruitment flier. Those patients interested in participating were provided a link to an online PsychData link to complete the informed consent and a HIPAA form. Once the patient participant provided

informed consent, they progressed to additional PsychData questionnaires to be filled out by the patient participant prior to their initial evaluation with their physical therapist. Information collected consisted of: baseline demographic information sheet, General Trust in Physician Scale, Trust in Physician Scale, PCAS, Wake Forest Scale, ODI, and NPRS. The online participant data collection allowed for blinding of the physical therapist throughout the study to the trust measurement scores. Patient participants received normal physical therapy evaluation and treatment as directed by the physical therapist. Upon completion of the initial visit, the patient participant completed the WAI-SR, Trust in Physician Scale, PCAS, and Wake Forest Scale through a second PyschData link. After completion of the second physical therapy visit, the participating physical therapist completed the PT Survey of Patient Connection and Engagement. Patient participants were blinded to the physical therapist's responses on this instrument. Patient participants continued to receive normal physical therapy as directed by the physical therapist working toward discontinuation of the current episode of care. The majority of the physical therapy encounters (80%) needed to have the initial physical therapist directly involved with the care of the patient participant to be eligible for data collection. If less than 80% of the visits have the direct care delivered by someone other than the initial physical therapist, that data was excluded from primary analysis. Upon discontinuation of the current episode of care or the end of 6 months of care, the patient participant completed the Trust in Physician Scale, PCAS, Wake Forrest Scale, WAI-SR, ODI, NPRS, and GROC. The participating physical therapist completed a second PT Survey of Patient Connection and Engagement at the conclusion of care. (Figure 1) Patient participants that complete all three series of forms (pre-initial visit, post-initial visit, and discontinuation episode) were eligible for a total of \$25 in Walmart gift cards to be mailed to an address of their choice.

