Once patient participants completed the informed consent process they were directed to a second PsychData link in order from them to complete a participant demographics form (Appendix B) that further verified their eligibility into the study. Inclusion criteria consisted of greater than 18 years of age, able to read, speak, and write in English, and presence of low back pain for at least 3 months. Exclusion criteria were current pregnancy or active cancer diagnosis. Patient participants were also excluded from the study if at any point during the episode of care they required different medical attention beyond physical therapy and needed to be referred out for medical reasons and had to discontinue their physical therapy prior to achieving goals. Any patient participant that did not receive at least 80% of the treatments from the initial physical therapist participant were excluded from primary data collection. Physical therapist participant inclusion criteria were having a physical therapy license to treat patients and employed at a clinic site approved for the study.

The initial *a priori* was set for a total of 64 patient participants with the primary complaint of chronic low back pain that had lasted a minimum of 3 months prior to initiating the current physical therapy episode of care. The patient were consecutively enrolled in the study at the various clinic sites. An *a priori* achieves 79% power to detect a Pearson correlation of 0.400 using a two-sided hypothesis test with a significance level of 0.05 with an included 20% dropout rate. These results are based on 1000 samples from the bivariate normal distribution under the alternative hypothesis. The number of physical therapist participants was determined by the clinic site enrollment and treating at least one patient participant during the course of the study.

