dimensions of trust (fidelity = #1-2, competence = #3-4 and #8, honesty = #6, global = #5, #7, and #9-10). The items cover question format consisting of a mixture of positive (#1, #4-7, and #9-10) and negative (#2, #3, and #8) statements in Likert categories (1 = strongly disagree, 2 = disagree, 3 = neutral, 4 = agree, 5 = strongly agree). Trust is measured with a sum of the 10 item scores, with reverse scoring for negative items, to produce a range of scores from 10 to 50, with higher scores demonstrating higher levels of trust. For purposes of this study the questions with the words “your doctor” were replaced with “your physical therapist”. The final Flesch reading ease is 54.0, demonstrating a Flesch-Kincaid grade level of 9.6 according to Microsoft® Word 365 for Office (Redman, WA). (Appendix E)

General Trust in Physician Scale: Patient general trust in healthcare providers has been shown to be different than interpersonal healthcare provider trust. Thus general trust potentially has a strong influence on the formation of interpersonal trust and was measured prior to the initial visit for the purpose of this study with the General Trust in Physician Scale. This scale was developed to test general trust in physicians in contrast to other scales that assess individual physician trust. An 11-item scale was formulated from the initial 25 candidate items that were based on five domains (fidelity, competence, honesty, confidentiality, and global trust). Five-point Likert scale categories were utilized for each question (1 = strongly disagree, 2 = disagree, 3 = neutral, 4 = agree, 5 = strongly agree). The final 11-items have both positive (#1, #3-6, and #8-10) and negative (#2 and #7) worded questions, with reverse scoring for negative items. Scores can range from 11 to 55, with higher scores demonstrating higher trust. If one or two scores were left out, the missing values were imputed with the average score, if three or more scores were missing the total score was not be calculated and left out. The words “physical therapists” were inserted for the word “physician” for use with this study. The General Trust in

Physician Scale according to Microsoft® Word 365 for Office (Redman, WA) has a Flesch reading ease of 42.4 providing a Flesch-Kincaid grade level of 10.8. (Appendix F)

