### Statistical Analysis Plan (SAP)

All data was coded and entered into SPSS version 27.0 (IBM Corp., Armonk, N.Y., USA) for statistical analysis. Patient participant and physical therapist participant demographic data was reported with means, ranges, and standard deviations. The primary correlational statistics was the Spearman rho to assess the various individual trust measurement scores and changes in scores over time and individual scores with the primary outcome measurements of pain, function, and global change. The individual trust measurement scores, that have not been used in physical therapy, were be analyzed for correlation to WIA-SR, which has been used in physical therapy research, with Spearman's rho. Friedman's analysis of variance looked at changes in individual trust measurement scores over time from pre-initial visit, post-initial visit, and discharge. The non-parametric analysis was used due to the ordinal nature of the outcome variables. The PT Survey of Patient Connection and Engagement was analyzed for correlation with outcomes and the individual trust measurement scales with the Spearman rho. Linear regression analysis was done with the individual trust measurement scales and outcomes variables for predictive modeling of trust and outcomes assessment.

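### Pre-visit provider-specific trust means expectation for first-contact patients and earned trust for returning ones, and no inferential analysis uses the recorded prior contact

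*Combined protocol and SAP*

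**What the plan says.** Section 3.3.5 lists the forms that patients complete "prior to their initial evaluation with their physical therapist". Besides demographics they are "General Trust in Physician Scale, Trust in Physician Scale, PCAS, Wake Forest Scale, ODI, and NPRS". The three provider-specific scales come round again after the first visit: "Upon completion of the initial visit, the patient participant completed the WAI-SR, Trust in Physician Scale, PCAS, and Wake Forest Scale". They are completed a third time at discontinuation or after 6 months of care. The alliance measure (WAI-SR) is not in the pre-visit set.

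Section 3.3.2 rewords all three scales to refer to the physical therapist. For the Wake Forest Scale, "the questions with the words “your doctor” were replaced with “your physical therapist". The same section treats general trust in providers as distinct from interpersonal trust, and measures general trust separately before the visit.

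Section 3.3.4 records "whether the patient had been seen in physical therapy previously, at this specific site, or by this specific therapist". Section 3.3.1 sets no criterion on prior contact: "Exclusion criteria were current pregnancy or active cancer diagnosis". The later exclusions concern referral out of physical therapy and the 80% same-therapist rule.

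The SAP reports demographics with means, ranges and standard deviations. It then plans Spearman correlations of trust scores and change scores with outcomes, a Friedman test of "changes in individual trust measurement scores over time from pre-initial visit, post-initial visit, and discharge", and linear regression of outcomes on trust. It names no covariate, stratum, subgroup or sensitivity analysis.

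**The concern.** There are two separate problems, with different reach.

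**Meaning.** The same questionnaire, asked before the visit, measures different things in the two kinds of patient. A pooled change from pre-visit to post-visit therefore combines expectation being replaced by experience with earned trust being updated. Reported as growth in trust, it would be ambiguous. This affects the pre-visit scores, any change taken from them, and the Friedman test that starts from them. Post-initial-visit and discharge scores are all taken after contact with the therapist and do not have this problem.

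**Confounding.** Prior contact may be related both to trust and to outcome. If so, it can create or mask a trust-outcome association at any time point, including after the first visit.

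Change in trust over time, and trust against outcome, are the study's main questions. The variable needed to separate these explanations is already collected.

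**Working it through.** **1. Evaluable number.** Section 3.3.1 plans 64 patients with 20% dropout: 64 × 0.80 = 51.2, so 51. The stated 79% power for a correlation of 0.400 (two-sided 0.05) is reproduced by a simulated Spearman test at n = 51, which gives 79.8%. A Pearson test at n = 51 gives 83.5% by Fisher's z. The power figure is not in dispute; it only fixes n = 51.

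**2. Assumptions for size.** The documents give no share with prior contact and no group differences. Everything below is therefore illustration:
- share with prior contact q = 10% or 30%;
- trust higher by d = 1 SD in returning patients;
- outcome different by e = 0.3, 0.5 or 0.8 SD in returning patients;
- no association between trust and outcome within either group.

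**3. Correlation produced by prior contact alone.** For the product-moment correlation,

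r = q(1−q)·d·e / √{[1 + q(1−q)d²]·[1 + q(1−q)e²]}

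Example with q = 0.3, d = 1, e = 0.8: q(1−q) = 0.21; the numerator is 0.21 × 0.8 = 0.168; the denominator is √(1.21 × 1.1344) = 1.172; r = 0.143.

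The planned statistic is Spearman's rho, so its mean and its rejection rate at two-sided 0.05 were simulated at n = 51:

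| Prior contact | Outcome difference (SD) | r (formula) | Mean Spearman | False positives |
|---|---|---|---|---|
| 10% | 0.3 | 0.026 | 0.024 | 5% |
| 10% | 0.5 | 0.043 | 0.039 | 6% |
| 10% | 0.8 | 0.067 | 0.060 | 7% |
| 30% | 0.3 | 0.057 | 0.055 | 7% |
| 30% | 0.5 | 0.093 | 0.089 | 10% |
| 30% | 0.8 | 0.143 | 0.139 | 16% |

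With e negative (returning patients do worse) the values have the same size and the opposite sign.

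**4. Does adjustment work?** In the same simulations the partial Spearman correlation given prior contact (yes/no) has mean about 0.00 and rejects in about 5% of studies in every row.

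**5. Change over time.** If first-contact patients rise by δ from pre- to post-visit and returning patients do not change, the pooled mean rise is (1−q)δ. With δ = 0.5 SD this is 0.45 SD at q = 10% and 0.35 SD at q = 30%. The pooled figure describes neither group and depends on an unreported mix.

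**The case against.** Four objections have force.

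- **Presence is not shown.** A reader might infer that returning patients did enrol and that the results are known to be contaminated. The documents do not support that. Section 3.3.1 describes recruiting new patients who are given new-patient paperwork. It does not define them as new to the therapist, so returning patients are permitted and the form foresees them, but they may have been few or none. With none, there is no mixing and no confounding by prior contact.

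- **The Friedman test is not made falsely significant.** A reader might infer that mixing manufactures a significant result. It does the opposite. Take n = 51, a 0.5 SD rise at the first visit in first-contact patients only, kept to discharge, and a within-person correlation of 0.5 (all assumed). Rejection falls from about 87% with no returning patients to about 29% when half are returning. First-contact scores do change in that scenario, so detecting change is correct. What stays open is what the change means, and for first-contact patients that question exists even with no returning patients.

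- **The direction of confounding is unknown.** It is tempting to say that patients who did well before come back with higher trust. The documents offer no evidence for this. Returning with chronic back pain could equally mark persistent symptoms and a worse outcome.

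- **A yes/no covariate is a partial remedy.** It removes a mean difference between the groups but does not make the pre-visit score mean the same thing in both. At 10% or 30% prior contact there would be about 5 or 15 returning patients among 51, too few for a precise interaction or separate correlation. This stands. It is why labelling and descriptive reporting by group are needed beside the covariate.

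Nor is it right to say the item is never used. The SAP's descriptive reporting of demographics may cover it; the gap is in the inferential analyses. The General Trust scale is properly asked before contact and is unaffected.

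**Conclusion.** The point holds in this limited form. The plan allows two kinds of patient whose pre-visit scores on the three provider-specific scales have different meanings. It records which kind each patient is, and it pools them in every stated inferential analysis.

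The problem of meaning is confined to pre-visit scores, changes from them and the three-point Friedman test. Confounding could extend to later trust-outcome associations. Its size cannot be known from the documents. Under the stated assumptions it is close to negligible at 10% prior contact and moderate at 30%. Even the largest value shown, 0.14, is small beside the 0.400 the study was sized to detect, and the sign could go either way.

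This does not show that the study's results are biased. It shows that a reader could not tell from the planned analyses whether they are. The correction should be made because it needs no new data; if the reported count proves to be zero or very small, the count largely settles the matter.

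**What to change.** Keep the data collection and change the SAP, or the reporting if analysis is already done:

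1. Report how many analysed patients had prior care by this therapist, using the existing demographics item (Appendix B).
2. Add that item (yes/no) as a covariate in each trust-outcome regression, and report the partial Spearman correlation beside the crude one.
3. Report pre-to-post-visit change separately for patients with and without prior contact, descriptively if the prior-contact group is small.
4. Label the pre-visit score of first-contact patients as expected trust.
5. Keep the three-point Friedman test for all patients. Add a paired comparison of post-initial-visit with discharge scores as the measure of change in experienced trust. It uses the same two time points for everyone, so the two groups do not end up with different baselines.

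Cost: SAP wording, one degree of freedom per model, and one further comparison for each of the three scales. The result in the prior-contact subgroup will be imprecise, and the covariate does not by itself resolve the difference in meaning of the pre-visit scores.

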## Study protocol

This dissertation was a non-experimental correlational quantitative analysis of multi-clinic site locations of consecutive patients referred to or coming via direct access for physical therapy care related to chronic low back pain. It was a collection of trust surveys, TA questionnaires, and patient reported outcomes related to their low back pain and function completed by the patient participant through an interrupted time-series of prior to initial evaluation, post-initial evaluation, and at discontinuation of the current episode of care. The physical therapist participants completed a patient connection and engagement questionnaire after the second visit and at discharge along with outcomes measurement data collect at the completion of the current episode of care. Data collection was at multiple outpatient physical therapy sites with multiple physical therapists and wide patient demographics to improve generalizability of the study findings.

The research project was conducted according to the Declaration of Helsinki. All the participants were fully informed of the study content before their participation in this study and completed informed consent. Institutional Review Board (IRB) at the University of South Dakota served as the IRB of record with joint approval from Nova Southeastern University IRB.

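### The second 80% continuity sentence in section 3.3.5 is inverted: as written it excludes the patients whom section 3.3.1 keeps

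*Combined protocol and SAP*

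**What the plan says.** The combined protocol and SAP states the continuity rule three times.

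- Section 3.3.1 (Participant recruitment) says that patients who "did not receive at least 80% of the treatments from the initial physical therapist participant were excluded from primary data collection".
- Section 3.3.5 (Procedural process) first says: "The majority of the physical therapy encounters (80%) needed to have the initial physical therapist directly involved with the care". The same sentence makes this a condition for the patient "directly involved with the care of the patient participant to be eligible for data collection".
- The next sentence of 3.3.5 says: "If less than 80% of the visits have the direct care delivered by someone other than the initial physical therapist, that data was excluded". It goes on to name the primary analysis as the thing from which the data are removed: "initial physical therapist, that data was excluded from primary analysis".

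The Statistical Analysis Plan section does not restate the rule or define an analysis set.

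On timing, the Study protocol section places the patient forms "prior to initial evaluation, post-initial evaluation, and at discontinuation of the current episode of care". Section 3.3.5 agrees. For the first series, after consent, "they progressed to additional PsychData questionnaires to be filled out by the patient participant prior to their initial evaluation with their physical therapist". For the second, "Upon completion of the initial visit, the patient participant completed the WAI-SR, Trust in Physician Scale, PCAS, and Wake Forest Scale".

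**The concern.** The third statement makes exclusion depend on the share of visits delivered by someone other than the initial therapist, and excludes when that share is low. A low share by others is a high share by the initial therapist, so the sentence removes the patients whom the other two statements keep.

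The study relates a patient's trust in a particular therapist to that patient's outcome, so continuity with that therapist decides who belongs in the primary trust-outcome correlations. Anyone looking for the rule that governs the primary analysis would arrive at the inverted sentence, because the other two statements speak of data collection and the SAP section is silent. Following it literally would give the wrong set of patients.

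The consequence is also worded inconsistently. The patient's share of visits for the whole episode cannot be known when the first two form series are completed. For those forms, a bar on data collection cannot operate; the rule can only remove data from the analysis.

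**Working it through.** The plan gives no computed figure to reproduce here, so the check compares the rules.

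**Inputs.** The threshold is 80% in all three statements (sections 3.3.1 and 3.3.5). Let s be the initial therapist's share of a patient's visits. Each visit is counted as either that therapist's or someone else's, so the share by others is 1 − s. The parenthetical 80% in the first 3.3.5 sentence is read as at least 80%.

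**Rules in terms of s.**

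- Section 3.3.1: exclude if s < 0.80, so keep s ≥ 0.80.
- Section 3.3.5, first sentence: eligible if s ≥ 0.80, so keep s ≥ 0.80.
- Section 3.3.5, second sentence as written: exclude if 1 − s < 0.80, that is s > 0.20, so keep s ≤ 0.20.

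**Comparison.**

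- s ≥ 80%: kept by 3.3.1, excluded by the literal sentence.
- 20% < s < 80%: excluded by both.
- s ≤ 20%: excluded by 3.3.1, kept by the literal sentence.

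**Illustration with an episode of 10 visits (assumed length).**

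| Visits by initial therapist | Share by others | 3.3.1 | 3.3.5 second sentence as written |
|---|---|---|---|
| 1 or 2 | 90% or 80% | exclude | keep |
| 3 to 7 | 70% to 30% | exclude | exclude |
| 8, 9 or 10 | 20%, 10% or 0% | keep | exclude |

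No value of s is kept by both rules, so applying all the sentences literally would leave an empty primary set.

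**After correction.** If the second sentence referred to care by the initial therapist (exclude if s < 0.80), all three statements would keep the same set, s ≥ 0.80.

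**The case against.** The strongest reply is that the documents already settle the direction. Two statements, one of them immediately before the faulty sentence, point the same way, and the literal rule makes no sense in a study of trust in the treating therapist. No analyst is likely to apply it. That is a good reason to grade the point as minor. It does not make the sentence correct.

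Three narrower objections have some force.

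- **The measures differ.** Section 3.3.1 counts treatments received from the therapist, the first 3.3.5 sentence counts encounters in which the therapist was directly involved, and the second counts direct care delivered. A visit shared with another clinician could count under one and not clearly under another. The working above sets this aside by counting each visit once. The difference deserves attention when the text is edited, but it does not touch the inversion.
- **The share may not be in the dataset.** Neither the demographic forms in 3.3.4 nor the forms listed in 3.3.5 include a therapist share or visit log, so the check may need clinic records. Still, the share had to be known to apply any 80% rule.
- **The phrase about data collection can be read as meaning the primary data set.** That reading is possible in 3.3.1, which states the exclusion in retrospect. Aligning the phrases is therefore a secondary tidy-up, though the timing of the forms supports it.

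**Conclusion.** The concern holds as a minor drafting error in operative text. The second continuity sentence in 3.3.5 reverses the rule, keeping s ≤ 20% where the other two statements keep s ≥ 80%.

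This rests on counting each visit as either the initial therapist's or another's, and on reading the first 3.3.5 sentence as a minimum of 80%. The opposition to 3.3.1 does not depend on the second assumption.

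The number of patients affected cannot be derived from the documents. It is zero if the exclusion ran in the intended direction, and nothing indicates otherwise. The 79% power printed in 3.3.1 does not depend on this sentence. Had the literal rule been applied, the number analysed, and so the power achieved, could have differed.

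**What to change.** 1. In 3.3.5, replace the second continuity sentence with the 3.3.1 criterion and the correct consequence: a patient with fewer than 80% of treatments from the initial therapist participant is excluded from the primary analysis.
2. In 3.3.1 and in the preceding 3.3.5 sentence, change the reference to data collection so that both name the primary analysis. While editing, confirm that all three statements count the therapist's share in the same way.
3. Check the direction of the exclusion as applied: the lowest initial-therapist share among patients in the primary set should be at least 80%. Re-run the primary analysis only if it is not.

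The cost is one sentence replaced, two phrases changed and one check. The check is short if the share was recorded with the study data, and longer if it has to be taken from clinic records. No re-analysis is needed if the exclusion ran as intended.
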